Selection of Subjects:

From the parent study, 42 participants will have 2 or more age and/or COVID-19 related social isolation risk factors (Table 2). These individuals will be randomized into the Parent study's WL-Protein arm (n=21) or the WL-Control arm (n=21)

Table 2. High-Risk Criteria Due to COVID-related Isolation (≥ 2)

Criteria	Definition
Isolated living environment	Lives alone or eats all meals alone
Risk of sarcopenia	Score of ≥ 4 on SARC-F screener
Poor access to medical care	$\leq 10\%$ Service connection
Sensory impairment	Hearing and/or visual impairments that impacts IADLs and/or ADLs
Caregiver burden	Caregiver for grandchildren, children, and/or spouse
Chronic pain	Moderate, severe, or very severe response to SF-36 pain question

Randomization: The following variables will be blocked in this order: 1) Race (white versus black, 2) chronic health conditions (≥ 3 versus <3), and 3) physical function, SPPB score (≥ 8 versus <8). An equal number of participants will be randomized across the two arms to end up with N=42.

Arm 1: High Risk Weight Loss Protein (HR-WL-Protein; n = 21 completers) 10% WL diet with 1.4g protein/kg body wt/day; ≥ 30 g high quality protein per meal

Arm 2: High Risk Weight Loss Control (HR-WL-Control; n = 21 completers) 10% WL diet with 0.8g protein/kg body wt/day

Screening (Two-step process):

Screening Visit Level 1: Confirm 2 or more high risk criteria (see Table 2), confirm $\text{BMI} \geq 30 \text{ kg/m}^2$, confirm SPPB score of 4-11, confirm fasting plasma glucose ≥ 95 and $< 126 \text{ mg/dL}$, confirm Mini-Cog ≥ 3 (or ability to complete all ADL's).

Screening Visit Level 2: Routine blood and urine chemistries and confirm age-normal renal status.

Aim 1:

Feasibility: Recruitment, retention, and intervention resources (defined in detail below)

Acceptability (6 months): participant satisfaction of intervention (defined in detail below)

Aim 2:

Physical Performance (0, 3, 6 months): Short Physical Performance Battery (SPPB) including three domains Balance (side-by-side, semi-tandem, tandem), gait speed (4-meter timed walk), and lower extremity strength (chair stands)

Anthropometrics: Body weights and body composition using Bod-pod.

Insulin Resistance: Glycated Hemoglobin (HbA1c), assessed in whole blood.

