This study will utilize a Request for HIPAA waiver of Authorization and waiver or alteration of informed consent process to identify potential participants for this research study. Each year of the study we will use the VA Informatics and Computing Infrastructure (VINCI) to conduct a query to identify Veterans seen at the Durham VAMC in the past year who were age ≥ 55 yrs, were obese ($BMI \geq 30 \text{ kg/m}^2$), and had prediabetes identified by either a HbA_{1c} between 5.7 and 6.4 % or a fasting blood glucose of ≥ 95 to $< 126 \text{ mg/dl}$. We will also work with the MOVE program coordinator, [name], and the Diabetes Management Clinic at the VA, to recruit patients who fit the above description. Finally, we will conduct face to face recruitment at VA organizations within the community and local libraries. We will also provide flyers to various VA clinics for providers and clinic staff to share with veterans. Potential clinics include primary care and specialty clinics at the Durham VA, Hillandale, Raleigh and Wake County, and Clayton clinics.

³ Participants enrolled after 10/1/2023 will have a goal of 5-10% reduction in body weight due to the shortened study period.

We will contact Veterans who meet inclusion criteria by mail via a recruitment letter signed by the PI that describes the study and emphasizes eligibility based on the fact that their prediabetes increases their risk for developing type 2 diabetes. In the letter, potential participants will call our office number and will be given an opportunity to “opt-out” and decline participation and/or further contact regarding participation. Five business days after the mailing, Veterans who have not called the study number to decline participation will be called by a study staff member to request their participation in the research study (see telephone screen script). Following a script, the recruiter will describe the study, query about potential exclusions and assess overall interest in participation. Interested and eligible subjects will then be scheduled for their first screening visit.

Additional recruitment methods include the advertisement of the study via third parties, including Facebook or Instagram, Craigslist, DukeList and Google ads. Advertisements will direct interested participants to contact the study team for more information about the study.

Consent Process

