On the day of the consent meeting, potential participants will be presented a full description of the study measurements, the interventions, and the randomization process. The participant will be told that their participation is voluntary, and they may choose not to answer any questions that they find too sensitive. Also, Veterans will be told that their participation will not affect their care at the VA. The study staff member will explain the study in detail. The participant will be given as long as they need to read through the consent form and HIPAA Authorization. Study staff will answer all questions and concerns. No study procedures will begin until formal, written informed consent has been obtained. This visit will determine if a participant is eligible to participate in the study. If a participant does not qualify, they will be given a letter indicating the reason of disqualification, and other resources/ programs for which they may qualify based on their condition. This visit will take place at the Duke Center for Living and will last approximately 90 minutes.

Adverse Events

All adverse events will be reported per Durham VAMC requirements. Given that the study population is older, somewhat functionally impaired and with metabolic risk factors, and based on our prior experience with a similar (non-Veteran) population, we anticipate that we will have adverse events, including one or more serious adverse events during the study period but that these adverse events will not be associated with the intervention, which is low risk. The most likely adverse event relating to the intervention would be a minor musculoskeletal injury during the exercise class. We will work to prevent this with close supervision by a trained exercise instructor and providing safety guidelines for when exercising at home. All Serious, Unanticipated and Related adverse events will be reported to the IRB within 5 business days of hearing of the event. All other adverse events will be reported at continuing review.

Costs and/or Payments to Subjects

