Power Estimate: The sample size of $n = 84$ per group is based directly on our findings in the MEASUR-UP study, which used the same diet treatments, study population, and primary outcome as in the present Aim 1. In MEASUR-UP, the SPPB score for WL-Pro changed by +2.4 units over the course of the study, while the WL-Control group experienced an increase of +0.9 units. The pooled standard deviation of these changes is 1.7. Thus, the MEASUR-UP study observed a standardized difference of $0.88 = (2.4 - 0.9)/1.7$. Differences of this magnitude have been labeled as 'large' in the power analysis literature. Assuming equivalent effect sizes observed in the MEASUR-UP study, an overall sample size of 100 (evenly divided between groups), and a Type-I error rate of 0.05 (two tailed), the power of our design is greater than 99% to declare significance for the effect size observed in the pilot. At 80% power, this design is powered to detect a difference in change scores in the SPPB of 0.96, or a standardized difference of 0.57.

Analysis Plan for the supplemental protocol:

Aim 1: Feasibility-Recruitment capability: Proportion of participants recruited will be calculated as the number of participants deemed potentially eligible and contacted for enrollment divided by the total number of

participants enrolled. Feasibility of recruitment hypothesis: ≥35% of participants approached for recruitment will agree to participate

Feasibility-Retention: Retention proportion retention will be computed by dividing the number of retained subjects at the end of the intervention by the total number randomized into the study.

Retention hypothesis: ≥80% of participants will remain in the study for the duration of the trial

We will calculate the rate of retention and its respective confidence intervals overall and by group. While non-powerful, we will assess if these rates differ by chi-square test of proportion and Poisson regression respectively. In a series of sensitivity tests, we will assess if retention overall was impacted by demographic and high risk variables.

Feasibility-Intervention Tools: Records of intervention tools and time spent to administer them will be used for post-study analysis of intervention tool effectiveness.

Acceptability-Satisfaction: participant satisfaction of intervention delivery, overall experience, and outcomes will be assessed using a Likert scale and open-ended questions.

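### The supplement's recruitment proportion is defined as contacted divided by enrolled, the inverse of the ratio its own ≥35% criterion needs

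*Combined protocol and SAP*

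**What the plan says.** The supplement's Aim 1 is feasibility (recruitment and retention) and acceptability. The supplement's measures list defers the feasibility definitions to later text, and the only recruitment formula in the document is under the analysis plan for the supplemental protocol, Aim 1. There the proportion recruited is "calculated as the number of participants deemed potentially eligible and contacted for enrollment divided by the total number of", and after a page break the sentence and its successor run on as "participants enrolled. Feasibility of recruitment hypothesis". The numerator is therefore those potentially eligible and contacted, and the denominator is those enrolled.

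The criterion follows at once: "≥35% of participants approached for recruitment will agree to participate".

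Retention, defined next, is found by "dividing the number of retained subjects at the end of the intervention by the total number randomized into the study", with the hypothesis that "≥80% of participants will remain in the study for the duration of the trial". That ratio is the right way up.

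Three other places bear on who is counted:

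- Subject Recruitment describes mailed letters and follow-up calls, then adds social media and web advertising: "Advertisements will direct interested participants to contact the study team for more information about the study".
- Consent Process says of the consent visit: "This visit will determine if a participant is eligible to participate in the study".
- The supplement's section on selection of subjects gives a total of 42, but describes each arm by completers, for example "HR-WL-Protein; n = 21 completers".

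**The concern.** A share of people approached needs the people approached in the denominator. The formula puts them in the numerator, so it does not compute the quantity that the 35% threshold refers to. An analyst who follows the formula would report a value of 100% or more as a proportion, and the worse the recruitment, the larger the value. An analyst who follows the criterion sentence could find that the same recruitment fell short.

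Correcting the direction leaves two counting questions open. The formula counts people enrolled, while the criterion counts people who agree to take part. Consent comes before eligibility is settled, so some Veterans can agree and never go on to the trial. The plan also does not say whether a Veteran who responds to an advertisement counts as contacted. If these choices are made after the counts are known, they could decide whether the threshold is met.

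**Working it through.** **Inputs from the document.** Written ratio: contacted / enrolled. Criterion: at least 0.35 of those approached agree. Supplement size: 42, also described as 21 completers per arm. Retention hypothesis: at least 80%. Parent trial's planning dropout: 30%.

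**Assumptions.** The document does not give the number contacted, so the contact counts below are illustrative. Enrolled stands in for agreeing, and approached for contacted.

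**The plan's own figure.** The 35% is a threshold and is not derived from other inputs, so there is nothing to reproduce.

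**Formulas.** Let C be the number contacted and E the number enrolled.

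- As written: W = C / E.
- As the criterion requires: R = E / C = 1 / W.

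If every enrollee was first contacted, C ≥ E and W ≥ 1, so W always exceeds 0.35. At an uptake of exactly 35%, W = 1 / 0.35 = 2.857.

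**Number enrolled.** If 42 is the number enrolled, E = 42. If 42 is a completer target, 80% retention gives 42 / 0.80 = 52.5, so 53 enrolled. The parent trial's 30% dropout gives 42 / 0.70 = 60.

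| Enrolled | Contacted (assumed) | Written: C / E | Criterion: E / C | Written ≥ 35%? | Criterion ≥ 35%? |
|---|---|---|---|---|---|
| 42 | 84 | 200% | 50% | yes | yes |
| 42 | 120 | 286% | 35.0% | yes | yes |
| 42 | 210 | 500% | 20% | yes | no |
| 42 | 420 | 1000% | 10% | yes | no |
| 53 | 151 | 285% | 35.1% | yes | yes |
| 53 | 152 | 287% | 34.9% | yes | no |
| 53 | 530 | 1000% | 10% | yes | no |
| 60 | 171 | 285% | 35.1% | yes | yes |
| 60 | 600 | 1000% | 10% | yes | no |

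With the ratio the right way up, the criterion is met with at most 120 contacted for 42 enrolled, 151 for 53, or 171 for 60. The written ratio meets 35% in every row.

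**Exception.** If self-referred enrollees are left out of the contacted count, C can be smaller than E. The written ratio falls below 0.35 only if C < 0.35 × 42 = 14.7, that is 14 or fewer contacted (14 / 42 = 0.333; 15 / 42 = 0.357). For 53 enrolled the bound is 0.35 × 53 = 18.55, that is 18 or fewer (18 / 53 = 0.340; 19 / 53 = 0.358).

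**Effect of the numerator after the inversion is corrected.** Assume 150 contacted, 55 agreeing and 42 enrolled. Counting those who agree gives 55 / 150 = 36.7%, which meets the threshold. Counting those enrolled gives 42 / 150 = 28%, which does not.

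**The case against.** The strongest reply is that this is a swapped phrase which the next sentence exposes. The criterion is complete in its own words: it names its denominator, does not depend on the formula, and can fail. The label of the measure and the correctly oriented retention ratio point the same way. No go/no-go decision, sample size or test hangs on the 35%, and confidence intervals and group comparisons are specified for retention only.

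Much of this stands. The intended direction can be inferred, the criterion sentence itself is sound, and the consequences stay within the supplement. But the formula is the only definition given for a named Aim 1 measure, and followed exactly it gives a wrong result. Leaving the analyst to infer the right ratio is not pre-specification.

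Two further points stand in part. First, the document does not use the word enrolled consistently. For the same October 2023 cut-off, the parent measurement table's footnote refers to consent, while the study-arms note and the supplement's footnote refer to enrolment. The section on risks and benefits, by contrast, places enrolment after screening. It is safer to say that the term is undefined than that the two numerators must differ. Second, mail and telephone are the main contact route and advertising is additional, so the self-referral question is secondary and the exception calculated above is remote.

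**Conclusion.** The concern holds. The written recruitment ratio is the reciprocal of the one the criterion needs. The page break inside the sentence does not alter that reading, and no other passage supplies a different formula. Provided every enrollee counts as contacted, the written value is at least 100% and meets 35% whatever the uptake. The criterion's ratio can be far below 35% on the same data, for example 10% against 1000% with 42 enrolled and 420 contacted. The contact counts are assumptions, but the inversion does not depend on them.

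The error is confined to one feasibility measure in the supplement. It should be corrected because that measure has a pre-specified threshold. It does not touch the parent trial's primary analysis or sample size. The undefined numerator and the handling of self-referrals are lesser gaps in the same definition.

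**What to change.** In the recruitment paragraph of the supplement's analysis plan, define the proportion recruited as the number enrolled divided by the number deemed potentially eligible and contacted, and compare that with 35%.

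In the same edit:

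- Choose one numerator, either those who agree (consent) or those enrolled, define it, and use it in both the formula and the hypothesis.
- Use one term for the denominator in place of contacted and approached.
- State whether Veterans who come through advertisements count, and treat them the same way above and below the line.
- State whether potentially eligible includes high-risk status. The supplement confirms that status at its first screening visit, and the recruitment query and letters do not mention it, so a high-risk numerator could otherwise be set against a general denominator.

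The core correction is one sentence, and with the counting rules it is a short paragraph. No new data are needed, provided that contacts and self-referrals are logged.

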Social isolation was recognized as a major threat to the health of older adults long before the Covid-19 pandemic, with as many as one third reporting being isolated and feeling lonely.^{54,54} As the pandemic is predicted to persist throughout 2020, there is growing concern that long periods of COVID-19 related isolation will foster negative physical and mental health outcomes and speed the progression of physical frailty.⁵⁵ Building upon our preliminary findings (described below) and evidence from a large body of established literature on social isolation, we characterized (Table 1) some of the most important risks being faced by our older Veterans and explored opportunities to use remote interventions to reduce obesity and restore their physical function despite their need to isolate.⁵⁶ The proposed research takes the next step by exploring the feasibility, acceptability, and effectiveness of our remote intervention in Veterans who are at especially high risk of further functional decline due to isolation. In our preliminary surveys, we identified "high risk characteristics" that may lead to greater social isolation. Using the same target population in the parent trial, we will specifically recruit and enroll Veterans

Table 1. Risks Imposed by Age- and COVID-19-Related Social Isolation¹

Loss or Lack of:	Aging-related Isolation	Pandemic-related Isolation
Social Interaction	✓	✓
Financial resources, income	✓	✓
Access to medical care	✓	✓
Access to food, cooked meals	+/-	✓
Opportunity to exercise safely	✓	✓
Fulfilling relationships	✓	+/-

¹The +/- symbol indicates that this may or may not be true, depending on circumstances/resources.

meeting these age and COVID-19 related social isolation risk factors in addition to the parent trial inclusion criteria. As explained in the Aims section, the feasibility and acceptability of the intervention for this cohort will be determined, as will the successful attributes and time demands of the specialized attention they will require from interventionists. Pilot data on the effectiveness of the Protein treatment relative to the Control for restoring physical function in this population will also be acquired.

Specific aims:

Aim 1: To evaluate the feasibility (recruitment and retention) and acceptability (participant satisfaction) of a virtual diet and exercise obesity intervention in Veterans at higher risk for negative physical and mental health outcomes during COVID-19 isolation.

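### The supplement's 35% recruitment criterion is about high-risk Veterans, but the recruitment steps described do not record high-risk status for men who decline, so the rate it yields is that of all Veterans approached

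*Combined protocol and SAP*

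**What the plan says.** The supplement's Aim 1 is "To evaluate the feasibility (recruitment and retention) and acceptability (participant satisfaction) of a virtual diet and exercise obesity intervention in Veterans at higher risk". High risk is defined in its Table 2 as at least two of six criteria: isolated living environment, SARC-F score, service connection, sensory impairment, caregiving, and the SF-36 pain item. The supplement's Selection of Subjects section gives the number: "From the parent study, 42 participants will have 2 or more age and/or COVID-19 related social isolation risk factors (Table 2".

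The Analysis Plan for the supplemental protocol sets the criterion: "Feasibility of recruitment hypothesis: ≥35% of participants approached for recruitment will agree to participate". Its base carries no high-risk restriction, and there is no rule for men who decline before screening.

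The steps that come before agreement are these:

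- **Record query (Subject Recruitment):** selects on age, BMI and prediabetes.
- **Letter (same section):** offers an opt-out; only men who have not opted out are telephoned, five business days later.
- **Call (same section):** the recruiter describes the study and will "query about potential exclusions and assess overall interest in participation".
- **Recruitment data (Privacy, Confidentiality, and Information Security):** identifiers, age, medical history, HbA1c, fasting glucose, and alcohol or drug history. No Table 2 item is named.

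Table 2 status then appears under Screening (Two-step process): "Screening Visit Level 1: Confirm 2 or more high risk criteria (see Table 2").

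**The concern.** A recruitment rate for a subgroup needs subgroup membership for everyone in its denominator, including those who say no. At the plan's own threshold, 65% of the men approached decline, and the described procedure collects nothing that would place them in or out of the high-risk group. Four of the six criteria (SARC-F, SF-36 pain, eating alone, caregiving) need the man's own answers.

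What can be computed is the share of all Veterans approached who agree. That is a legitimate figure, but it describes recruitment to the parent trial's population. Reporting it as evidence that high-risk, isolated Veterans can or cannot be recruited would not follow. Recruitment is one of only two numerical feasibility criteria in the supplement, the other being 80% retention.

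**Working it through.** The 35% is a set criterion, not derived from other figures, so there is nothing to reproduce. The question is how far the overall rate can differ from the high-risk rate.

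**Inputs**

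- Threshold: 0.35 (Analysis Plan for the supplemental protocol).
- High-risk men: 42 (supplement, Selection of Subjects).
- All men: 112 (parent Design section). Both 42 and 112 are completer targets, so they are on the same footing: 42/112 = 37.5%. At the parent's 30% dropout, 42/0.70 = 60 and 112/0.70 = 160, and 60/160 is again 37.5%.
- Share *s* of decliners who are high-risk: not in the documents. Assumed range 25% to 50%, with the extremes shown.

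**Illustration.** Treat 112 as the number enrolled, and treat agreeing and enrolling as the same event. For the overall rate to sit exactly on the threshold, men approached = 112/0.35 = 320, and decliners = 320 − 112 = 208.

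High-risk rate = 42 / (42 + *s* × 208)

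| Assumed *s* | High-risk decliners | High-risk approached | High-risk rate |
|---|---|---|---|
| 25% | 52 | 94 | 44.7% |
| 37.5% | 78 | 120 | 35.0% |
| 50% | 104 | 146 | 28.8% |
| 100% | 208 | 250 | 16.8% |

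At *s* = 0 the rate is 42/42 = 100%. With every decliner unclassed, the data therefore bound the high-risk rate only between 16.8% and 100%.

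The break-even is *s* = 78/208 = 37.5%, the same as the high-risk share among those enrolled. The overall rate equals the high-risk rate only if high-risk men decline as often as the others, which is part of what Aim 1 is meant to find out. The result depends on the two shares and the overall rate, not on the counts, so using 60 and 160 in place of 42 and 112 gives the same rates.

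**Separate from the inverted ratio.** The same paragraph writes the recruitment proportion as the "number of participants deemed potentially eligible and contacted for enrollment divided by the total number of" men enrolled. At 35% uptake that gives 1/0.35 = 2.86, which cannot be compared with 35%. Turning it the right way up leaves the present problem unchanged.

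**The case against.** The strongest reply is that the telephone screen script is cited but not in the documents. Subject Recruitment says that interested and eligible men are scheduled for screening, so some eligibility is judged on the call, and the script may ask Table 2 items. The word confirm at Screening Visit Level 1 is also applied to BMI and fasting glucose, which the query has already selected on, so it does not show that high-risk status is first ascertained there. The supplement's Background says "we will specifically recruit and enroll Veterans" with the isolation risk factors, and the recruitment proportion refers to men deemed potentially eligible, which could be read as including Table 2. All of this stands, and it is why the point is conditional on the script. It does not remove the point. Men who opt out by letter have no screening call, and service connection from the record would settle at most one of the two criteria required. The analysis plan would still need a high-risk denominator and a rule for unknowns.

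It is also fair that nothing formal hangs on the criterion: this is a feasibility study, with no go/no-go rule tied to the 35%.

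A reader might infer something stronger: that the rate cannot be scored at all, or that the target is out of reach because 42 of about 160 is 26%, so high-risk recruits would be 0.35 × 0.2625 = 9% of men approached, and overall agreement would have to be 0.35/0.2625 = 133%. The documents do not support this. It divides a completer target by an enrolment figure; like for like, the share is 37.5%, giving 0.35 × 0.375 = 13.1% and 0.35/0.375 = 93%. It also puts only high-risk joiners over all men approached, a ratio the plan nowhere states. A man who agrees but lacks two criteria has still agreed.

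**Conclusion.** The point holds in conditional form. On the procedures described, and unless the script already asks the Table 2 items, men who decline cannot be reliably classed; letter opt-outs mostly cannot be classed in any case. The 35% criterion then measures agreement among all Veterans approached. In the illustration, an overall rate of exactly 35% is compatible with a high-risk rate of 44.7% or 28.8%, so the pass or fail for Aim 1's own population turns on a quantity the plan does not collect. That size rests on the assumed range for high-risk decliners and on the completer targets as the enrolled mix.

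The consequence is limited to what the supplement may conclude about recruiting high-risk men. The parent trial's primary analysis is unaffected.

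**What to change.** For men still to be approached:

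1. Ask the Table 2 items early in the existing call, before asking whether the man wishes to take part, and take service connection from the VA record. Update the recruitment waiver's data list if needed.
2. Log high-risk status as yes, no or unknown for everyone approached. Letter opt-outs, men who end the call early, and men approached before the change are unknown.
3. Define the rate as high-risk men who agree divided by high-risk men approached, with the ratio the right way up, and report bounds that count all or none of the unknowns as high-risk.

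If the script already asks these items, only steps 2 and 3 are needed. If it does not and will not be changed, one sentence suffices: the 35% is the agreement rate of all Veterans approached, and no recruitment conclusion specific to high-risk Veterans will be drawn from it. As this protocol version is dated 11/30/2023, many men may already have been approached, and that fallback may be the realistic choice.

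The cost is a slightly longer call, a possible waiver amendment, and wide bounds if many men are of unknown status. No extra participants are needed.
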